2.7. Data analysis plan

Our team has extensive experience in the use of web-based assessment, data management and data analysis. Quantitative data will be entered into an online encrypted, HIPAA-compliant data management system, REDCap, with secure access for unique study IDs assigned to each participant. REDCap survey data is then ready for download by study staff and will be imported into SPSS for data cleaning and analysis. CGM data will be downloaded via Dexcom Clarity and LibreView which create a CSV file for transfer to REDCap and data analysis programs.

Demographic, medical, psychosocial variables, and some outcome measures are surveys and multi-item scales that participants will answer in REDCap. Psychometric properties of scales will be assessed before proceeding to investigate the proposed aims. These psychometric properties include item-total correlations and Cronbach's α to assess reliability. Total scores and subscale scores, when available, will be calculated and used for statistical analyses. Descriptive statistics will calculate frequencies, means and standard deviations for study variables. Independent samples t-tests and χ^2 analyses will assess potential differences between groups at baseline in demographic, psychosocial and diabetes variables. Analyses for Hypotheses 1&2 will follow the intention-to-treat principle.

To test Hypotheses 1&2, we will first conduct a treatment group comparison (ONBOARD vs. CGM-only) of the change in A1c, the primary outcome, from baseline to 3, 6, and 12 months. Specifically, we will use linear mixed models to model changes in A1c as a function of time, intervention assignment, and group-by-time interaction. These models will include a subject-specific random effect to account for the correlation of

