outcomes over time within a subject. We will examine change from baseline for each outcome as the dependent variable. We will begin by fitting models with minimum covariates prior to considering additional covariates. Similar models will be used to examine secondary outcomes of time in range, days of CGM wear (Hypothesis 1), diabetes distress, and perceived CGM benefit (Hypothesis 2). We will reference information criteria (e.g., Akaike's) to inform model selection decisions. Beyond testing the groups-by-time interaction term, custom contrasts will assess group differences at each time point. Exploratory analyses will examine differences between subgroups over time after primary, intent-to-treat analyses are completed. Additional exploratory analyses will examine patient-level predictors of CGM wear (e.g. age, gender, diabetes duration). For the CGM-continuer subgroup, we will conduct exploratory longitudinal analyses using CGM data to look at changes in time in range. We will adjust for multiple comparisons by using the Benjamini-Hochberg procedure and a false discovery rate of 0.05 (78). Analyses will initially be conducted without imputation for missing values, using the missing-at-random approach (79) and then multiple imputation will be used to supply values for missing data. We will conduct sensitivity analysis by multiple imputation to compare the effects.

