3.7. Study stopping criteria

Individual subjects will be removed from the study for the following reasons: pregnancy, study-related adverse events (i.e. severe hypoglycemia, loss of consciousness, hypoglycemia related seizure, DKA related to study-related event requiring hospitalization), severe skin infection requiring systemic antibiotics, severe reaction to sensor tape, or other reasons that develop during the study that in the judgment of the investigator make it unadvisable for the subject to continue with the study

CHAPTER 4: MISCELLANEOUS CONSIDERATIONS

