4.4. Subject withdrawal

Participation in the study is voluntary and a subject may withdraw at any time. The investigator may withdraw a subject who is not complying with the protocol. For subjects who withdraw, their data will be used up until the time of withdrawal.

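### The only planned missing-data sensitivity analysis is unspecified multiple imputation, which as standardly done assumes missing at random like the main model and so cannot show whether the A1c result depends on that assumption

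*Combined protocol and SAP*

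**What the plan says.** Section 2.7 (Data analysis plan) sets out the main analysis of A1c: "we will use linear mixed models to model changes in A1c as a function of time, intervention assignment, and group-by-time interaction", with a random subject effect and change from baseline as the dependent variable. It adds: "Analyses for Hypotheses 1&2 will follow the intention-to-treat principle".

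The missing-data plan follows in two sentences. Analyses are first run without imputation, "using the missing-at-random approach (79) and then multiple imputation will be used to supply values for missing data". Then: "We will conduct sensitivity analysis by multiple imputation to compare the effects". No imputation model, auxiliary variable, delta adjustment, tipping point, pattern-mixture model or reference-based rule appears anywhere in the document.

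Three other places bear on why data go missing:
- Section 3.7: "Individual subjects will be removed from the study for the following reasons: pregnancy, study-related adverse events". The examples listed there include severe hypoglycemia and DKA.
- Section 4.4: "The investigator may withdraw a subject who is not complying with the protocol". The same section uses a withdrawn participant's data only up to withdrawal.
- Section 2.3 requires active CGM use for 12 weeks in both groups.

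The sample-size paragraph of section 2.7 expects 15% attrition.

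**The concern.** A sensitivity analysis for missing data should show what happens to the result if the main assumption is wrong. Here the assumption is that, given what was observed, participants with missing A1c would have followed the same course as similar participants who stayed. The mixed model relies on it, and so does multiple imputation in its usual form. If the two agree, a reader may take the result as robust to missing data when the assumption has not been varied.

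The assumption is open to doubt in this trial. Some exits are triggered by glycemic events or by not using the device, and assessments fall only at 0, 3, 6 and 12 months. A participant who leaves before month 3 has only a baseline A1c, so the observed A1c values may not explain the exit. Follow-up A1c also depends on mailed kits (section 2.2), and returning a kit may go with engagement.

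**Working it through.** **Inputs.** From section 2.7: 89 randomized per arm, 15% attrition, 76 completers per arm, d = .35, A1c SD 1.2 (with 1.0 thought more likely), correlation .50, and 0.5% as the minimum clinically significant difference. Assumptions of this check: two-sided 0.05, the sizes of departure, and a standard error held fixed.

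**1. The plan's own attrition figure.** 89 × 0.85 = 75.65, about 76 per arm, so about 13 per arm are missing. The figure reproduces.

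**2. Shift from a departure.** Let p be the missing share, equal in both arms, and δ the amount by which missing A1c is worse than missing at random predicts. The between-arm difference moves by

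p × (δ in ONBOARD − δ in CGM-only).

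With p = 0.15 and a net departure of 0.5%: 0.15 × 0.5 = 0.075%. With a net departure of 1.0%: 0.15%. If both arms depart equally, the shift is zero.

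**3. Tipping point at one visit.** SE = SD × √(2/76), and the tipping value is (observed difference − 1.96 × SE) / p. The 0.42% difference is d = .35 × SD 1.2.

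| SD | SE | Observed difference | Tipping value, p = 0.15 |
|---|---|---|---|
| 1.2 | 0.195 | 0.50% | (0.50 − 0.382)/0.15 = 0.79% |
| 1.2 | 0.195 | 0.42% | (0.42 − 0.382)/0.15 = 0.26% |
| 1.0 | 0.162 | 0.50% | (0.50 − 0.318)/0.15 = 1.21% |

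The documents give no larger attrition figure. If 27% were missing, the 0.50% rows would tip at 0.44% (SD 1.2) and 0.67% (SD 1.0). The 27% is borrowed from the CGM discontinuation rate in section 1.2.2. Stopping CGM is not the same as a missing A1c, so this is only an upper illustration.

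**4. Can the planned comparison reveal a departure?** A simulation used 89 per arm, SD 1.2, correlation .50, a true difference of −0.5, 15% missing at 12 months and 2,000 replicates. Both methods used all earlier A1c values.

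| Setting | Full data | Likelihood | Imputation |
|---|---|---|---|
| Missing at random | −0.505 | −0.506 | −0.506 |
| Missing ONBOARD A1c 1.0% worse than predicted | −0.352 | −0.498 | −0.497 |

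In the second setting both methods miss a bias of about 0.15%. Within a trial they differ by about 0.011% on average, the same as when missing at random holds. Their agreement carries no signal about the assumption.

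**5. What the comparison can reveal.** The planned dependent variable is change from baseline, with minimum covariates first. A participant lost before month 3 has no change score and drops out of that model, whereas imputation can use the baseline A1c. A second simulation used a 3-month contrast, 89 per arm, SD 1.2, correlation .50, a true difference of −0.42 and about 15% lost. ONBOARD loss depended only on baseline A1c, and control loss was random. The change-score analysis gave −0.33, imputation using baseline −0.42, and full data −0.42. The reason is that, with equal SDs and correlation .50, change has slope 0.5 − 1 = −0.5 on baseline, so selective loss on baseline biases the unadjusted change. Here the two analyses disagree, and usefully so.

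**The case against.** The strongest reply is that the planned comparison has value. Step 5 shows that imputation using baseline A1c can expose a missing-data problem that the change-score model hides. CGM wear, listed in Table 4, could also make missing at random more credible. This stands. A reader might infer that the two analyses must agree by construction, or that the comparison checks nothing. The documents support neither, because they specify no imputation model. For the same reason, the assumption behind the imputation is inferred from standard practice and is not stated in the plan.

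Second, the withdrawal rules do not prove that missingness depends on unobserved A1c. Device wear and severe events are recorded, the rules apply to both arms, and section 3.6.2 does not anticipate severe events. Participants may also stop CGM after 12 weeks and still return A1c kits. This stands too: the rules make a departure plausible, not established.

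Third, a reader might infer that the plan overstates the ONBOARD effect if its leavers do worse than its stayers. That does not follow. Bias in that direction needs ONBOARD leavers to do worse than their observed data predict, and by more than control leavers do. Severe hypoglycemia does not imply a higher A1c, so even the sign is open. Nor does a loss of power follow: the plan's power claim concerns repeated measures over three follow-ups, and the single-visit figures above do not speak to it.

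Fourth, for an observed 0.5% difference at 15% missing, the tipping values of 0.79% and 1.21% exceed the plan's own clinically significant difference. That is reassuring for an effect of that size. It is much less so for 0.42% at SD 1.2, where the value is 0.26%.

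None of these replies supplies an analysis that varies the missing-at-random assumption.

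**Conclusion.** The point holds in this form: the plan has no analysis that departs from missing at random, and the one labelled as sensitivity analysis cannot show whether the A1c conclusion depends on that assumption. It can check modelling choices and the information used, once its imputation model is stated.

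The possible effect is modest for a clear result and material for a borderline one: 0.075% per 0.5% of net departure at 15% missing, with the single-visit tipping values running from about 0.26% to 1.21% across the three cases shown. These values assume a single visit, 76 per arm, equal missing shares and a fixed standard error. They illustrate scale and do not predict bias, and the direction is not known in advance. This should be changed before analysis, but it does not undermine the design or the primary model.

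**What to change.** In section 2.7:
1. State that the missing-at-random mixed model is the primary analysis; the present order of un-imputed and then imputed analyses leaves this unclear.
2. Specify the imputation model: baseline A1c, arm, all observed visits and CGM wear.
3. Add delta-adjusted imputation, with the departure varied separately in each arm, and report the tipping point at which the conclusion changes.
4. Include, as one scenario, imputation of missing ONBOARD values from the CGM-only arm.
5. Apply the same to diabetes distress, which section 2.1 names as the primary endpoint of the psychosocial set, with that scale's own values in the imputation model.

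The cost is a paragraph of text, a few extra imputation runs, and the chance of having to report a less robust result. Sample size, data collection and the primary model are unchanged.

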2.8. Expected duration of study participation

Duration of study participation is expected to be 1 year.

CHAPTER 3: ADVERSE EVENT REPORTING AND SAFETY MONITORING

3.1. Overview of Safety Monitoring

Safety monitoring will be performed by Drs. [name] (PI) and [name] (Mentor) on an ongoing basis. Safety data will be gathered and reviewed periodically by the study investigators. Reviews will occur every two months during the course of the trial and the study staff will examine occurrence of adverse events and whether participants are satisfied with their participation. The PI will be responsible for evaluating each unanticipated problem and determining whether it affects the risk/benefit ratio of the study and whether modifications to the protocol and consent forms are required. The PI will be responsible for reporting unexpected problematic events involving any aspect of the study to the NIH and local IRB per institutional guidelines. Unanticipated problems to be assessed include adverse events, deviations from the study protocol, problems with informed consent, and confidentiality violations. The PI will report unanticipated problems to the NIH and IRB within 3 business days of their occurrence. The local IRB will review such cases and determine what actions must be taken to address or resolve the situation. As this study employs an FDA-approved device and the team is providing additional support, it was determined that there is no need for a Data Safety and Monitoring Board (DSMB).

3.2. Definition of an Adverse Event

Reportable adverse events in this study include any untoward medical occurrence that meets criteria for a serious adverse event or any medical occurrence (expected or unexpected) in a study participant that is study-related.

Hypoglycemic events are recorded as adverse events if the event required assistance of another person due to altered consciousness and required another person to actively administer carbohydrate, glucagon, or other resuscitative actions. This means that the subject was impaired cognitively to the point that he/she was unable to treat his or herself, was unable to verbalize his or her needs, was incoherent, disoriented, and/or combative, or experienced seizure or coma. These episodes may be associated with sufficient neuroglycopenia to induce seizure or coma. If plasma glucose measurements are not available during such an event, neurological recovery attributable to the restoration of plasma glucose to normal is considered sufficient evidence that the event was induced by a low plasma glucose concentration.

Hyperglycemic events are recorded as adverse events if the event involved diabetic ketoacidosis (DKA), as defined by the DCCT, and had all of the following:

- Symptoms such as polyuria, polydipsia, nausea, or vomiting;
- Serum ketones $> 1.0 \text{ mmol/L}$ or large/moderate urine ketones;
- Either arterial blood pH < 7.30 or venous pH < 7.24 or serum bicarbonate < 15 ; and
- Treatment provided in a health care facility

Skin irritation from sensor wear will be recorded in specific sections of the case report forms. An adverse event form is only completed if skin irritation is severe.

Distress or discomfort experienced by participants as they complete surveys is not considered an adverse event. However, we have trained psychologists on staff who will be available to address any distress or discomfort and initiate referrals if requested.

3.2. Recording of adverse events

Throughout the course of this study, all efforts will be made to remain alert to possible adverse events or untoward findings. The first concern will be the safety of the participant, and appropriate medical intervention will be made.

The investigator will elicit reports of adverse events from the participant at each visit and phone call and complete all adverse event forms online. The study investigator will assess whether an adverse event is related or unrelated to the study by determining if there is a reasonable possibility that the adverse event may have been caused by the study procedures.

The intensity of adverse events will be rated on a three-point scale: (1) mild, (2) moderate, or (3) severe. It is emphasized that the term severe is a measure of intensity: thus a severe adverse event is not necessarily serious. For example, itching for several days may be rated as severe, but may not be clinically serious.

Adverse events that continue after the participant's discontinuation or completion of the study will be followed until their medical outcome is determined or until no further change in the condition is expected.

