2.2. Study procedures

Participants will be recruited at Stanford University through a combination of in-clinic, in community locations and online through type 1 diabetes online communities. Eligible participants will be adults (ages 18-50) who have not been using CGM consistently (>5 days/week) for at least the past 6 months. Once identified in clinic or once someone has expressed interest in the study, study staff will approach potential participants to explain the study, determine eligibility, and obtain informed consent. All participants will complete their baseline visit remotely. This baseline visit will include 1) completing a hemoglobin A1c test kit that is mailed to them in advance; 2) completing a baseline assessment survey online via a secure site (REDCap) to obtain demographic and psychosocial data and 3) initiate use of CGM supplies. Participants will be given the choice of using Dexcom G6 or Libre 2 CGM. Participants will be mailed 12 weeks of CGM supplies of their choice and will receive initial standard CGM introduction and education from the study staff and will be provided with standard resources from the device manufacturer at this baseline visit. At baseline, participants will then be randomized. We will randomize at a 1:1 ratio, intervention to control. Those randomized to the intervention (ONBOARD) condition will schedule 4 60-minute sessions with study interventionist (every 2 weeks), with the first session scheduled for 2 weeks after CGM initiation. Sessions will be conducted via a secure, HIPAA-compliant, videoconferencing software (Zoom) and may be recorded to ensure consistency and quality of the intervention across participants and interventionists. Each participant will receive one unique Zoom link that they will use for all 4 of their study sessions. At the 3-, 6-, and 12-month time points, participants will be mailed A1c test kits for follow-up A1cs, and will complete a follow-up REDCap survey at these time points as well. The follow-up survey will assess psychosocial variables, technology satisfaction, and changes to demographic/medical information. Each follow-up survey is expected to take 30 minutes to complete. Of note, all study participants will

receive instruction on how to work with their insurance to obtain coverage for continuing to use CGM after the first 12 weeks of the study. At the 3-, 6-, and 12-month timepoints, CGM data downloads will be obtained.

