2.3. Study groups

There are two groups in this study: intervention (ONBOARD) and control (CGM-only). All participants will receive 12 weeks of CGM supplies and will receive standardized education about getting started with CGM. A person trained in delivering education about CGM will deliver education about CGM use and will be present during a virtual meeting while participant is inserting first sensor during training. This individual will be available to assist with questions from participants. In addition, Dexcom and Abbott representatives are available to participants for technical questions or issues with the system, just like the access any CGM user has. All participants in both groups will be required to actively use CGM for 12 weeks. After that time period, they can continue or discontinue use of CGM. If they decide to continue, the study team will provide information on working with insurance and with their provider to obtain CGM for both study groups.

After randomization, participants in the intervention group will receive 4 one-on-one sessions of ONBOARD (OvercomiNg Barriers & Obstacles to Adopting Diabetes Devices). Sessions will be held every 2-3 weeks over the 12-week period

when participants are using CGM provided by the study. ONBOARD is a multicomponent intervention to provide tailored support for CGM adoption. Session content and strategies are outlined in Table 3. Sessions target four primary topics. Each participant will receive content in the same order, but the program is designed to be flexible depending on individual barriers and concerns. Some participants may spend more time on certain topics than others. ONBOARD will approach CGM data interpretation

Table 3. ONBOARD Intervention Topic Content			
Barrier addressed	Topic name	Strategies used	Goals
	Introduction	- Psychoeducation; rapport building	
 - Provide rationale for ONBOARD - Introduce concepts from Technology Acceptance Model to discuss CGM pros and cons
Physical	Wearing Diabetes Device(s)	- Experiential wear	
 - Troubleshooting device placement - Provide education and examples of problem solving for common concerns and strategies for navigating them: appearance, insertion, skin irritation, discomfort, interference with daily activities - Provide resources for adhesive, skin prep, and adhesive removal

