2.5. Study visits and assessments

All participants will attend a baseline study visit. Baseline is the date they complete their first assessment and begin using their CGM and will receive training from study staff on beginning to use CGM. After baseline, only participants randomized to ONBOARD will receive 4 additional study visits. Remaining assessments (A1c, CGM data downloads, and surveys) will be done via mail and electronically, respectively.

Study assessments for both groups will occur at baseline, 3 months, 6 months and 12 months post-baseline. We will conduct these assessments and obtain glucose data to examine changes over time in glycemic and psychosocial variables. Participants will receive a \$25 gift card for each assessment they complete.

Assessment components are included in Table 4.

Table 4. Study Measures

Domain	Measure	Description	0 mos	3 mos	6 mos	12 mos
Demographic	History questionnaire	Medical, personal, device history	X			
	Demographic/medical update	Changes to baseline information		X	X	X
Psychosocial	Diabetes Distress Scale-T1D	28-item validated measure of T1D distress in adults	X	X	X	X
	Fear of Hypoglycemia - Worry	18-items; measure of fears related to severe low BG	X	X	X	X
	Hypoglycemic Confidence Scale	9 items; validated for adults with T1D	X	X	X	X
	Diabetes Self-Compassion Scale	19 items; validated for adults with T1D	X	X	X	X
	Patient Health Questionnaire-8	8 items; assesses depressive symptoms	X	X	X	X
	GAD-7	7 items; assesses anxiety symptoms	X	X	X	X
	Perceived Stress Scale	10 items; assesses stress and coping in past month	X	X	X	X
	World Health Organization-5	5 items; assesses emotional wellbeing	X	X	X	X
	Self Care Inventory-Revised	15 items; measure of a range of self-care activities	X	X	X	X
	Social Support Questionnaire	6 items; assesses availability of social support	X	X	X	X
Technology-specific	Diabetes Empowerment Scale-SF	8 items; assesses diabetes self-efficacy	X	X	X	X
	COVID-related impacts	Assesses general and diabetes-specific impacts of pandemic	X	X	X	X
	INSPIRE survey	Assesses closed loop attitudes	X			X
	Glucose Monitoring System Satisfaction Survey (GMSS-T1D)	15 items; validated measure of glucose monitoring device-related treatment satisfaction and quality of life	X	X	X	X
	Barriers to device use	19-item list of barriers	X	X	X	X
	A1c	Glycemic control	X	X	X	X

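### Adverse events are elicited only at visits and phone calls, but after baseline only ONBOARD has scheduled visits (4 versus 0), so non-serious study-related events are likely to be recorded more completely in ONBOARD

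*Combined protocol and SAP*

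**What the plan says.** Section 3.2 (Recording of adverse events) gives the only operational collection rule: "The investigator will elicit reports of adverse events from the participant at each visit and phone call". The same section adds a general commitment to stay alert to untoward findings, without a procedure.

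Section 2.5 sets the contacts: "After baseline, only participants randomized to ONBOARD will receive 4 additional study visits". For everything else it says: "Remaining assessments (A1c, CGM data downloads, and surveys) will be done via mail and electronically, respectively". Both arms attend the baseline visit, but that is when CGM begins.

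Section 2.2 describes the follow-up survey sent to both arms: "The follow-up survey will assess psychosocial variables, technology satisfaction, and changes to demographic/medical information". Table 4 lists a demographic/medical update and a 19-item barriers list, among others, but no adverse-event or skin instrument.

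Session timing comes from section 2.2 ("with the first session scheduled for 2 weeks after CGM initiation", then every 2 weeks) and section 2.3 ("Sessions will be held every 2-3 weeks over the 12-week period"). Skin problems are also session content. Table 3 includes "strategies for navigating them: appearance, insertion, skin irritation, discomfort, interference with daily activities".

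Section 3.2 (Definition of an Adverse Event) makes any study-related medical occurrence reportable, serious or not. Skin irritation goes to dedicated case report form sections, and an adverse-event form is added only when it is severe. Section 3.1 sets the oversight: "Reviews will occur every two months during the course of the trial and the study staff will examine occurrence of adverse events".

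**The concern.** Both arms wear the same sensors for 12 weeks and face the same skin and glycemic risks from them. How completely those events are recorded should not depend on the arm. Under the written rule it does, because scheduled asking is tied to visits and visits are part of the intervention. ONBOARD participants are also prompted about skin irritation by the session content.

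Three uses of the safety record are exposed:

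- Any description of harms by arm would partly reflect who was asked, and could make ONBOARD look worse for that reason alone.
- The two-monthly review, which stands in place of a DSMB, would receive scheduled enquiry from one arm only.
- The removal criteria in section 3.7, which include severe skin infection and severe reaction to sensor tape, act only on events that staff know about. They may be applied less completely in CGM-only.

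Mild events that nobody asked about are hard to recover afterwards.

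**Working it through.** **Step 1. Scheduled post-baseline enquiries.** Inputs: 89 randomized per arm (sections 2.6 and 2.7), 4 visits in ONBOARD and 0 in CGM-only (section 2.5), and no scheduled phone calls.

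- ONBOARD: 89 × 4 = 356. CGM-only: 89 × 0 = 0.
- At the 76 per arm expected after attrition: 76 × 4 = 304 against 0.

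These are scheduled enquiries only. Unscheduled calls would add to either arm by an unknown number.

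**Step 2. When the asymmetry operates.** Sessions start at week 2. Every 2 weeks gives weeks 2, 4, 6, 8; every 3 weeks gives weeks 2, 5, 8, 11. The imbalance therefore lies between about weeks 2 and 11, within the 12 weeks when CGM use is required. After that neither arm has scheduled enquiry.

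**Step 3. What the two-monthly review sees.** Two months is 365.25 / 6 / 7 = 8.7 weeks, so about 6 reviews fall in one participant's year. Counted from the participant's own baseline, sessions fall in about the first 1 to 2 of them in ONBOARD; scheduled enquiry reaches 0 in CGM-only. Section 3.1 schedules reviews over the trial as a whole, so this is a per-participant illustration.

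**Step 4. Illustrative size.** The documents give neither event rates nor detection probabilities, so both are assumed here, with equal true rates in the two arms.

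Recorded people = 89 × true rate × detection probability, with detection in ONBOARD set at 0.90.

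| Event type | True rate | CGM-only detection | ONBOARD recorded | CGM-only recorded | Gap |
|---|---|---|---|---|---|
| Needs an adverse-event form | 1% | 0.60 to 0.75 | 0.80 | 0.53 to 0.67 | 0.27 to 0.13 |
| Needs an adverse-event form | 5% | 0.60 to 0.75 | 4.01 | 2.67 to 3.34 | 1.34 to 0.67 |
| Any skin irritation, if recorded at visits | 10% | 0.30 to 0.75 | 8.0 | 2.7 to 6.7 | 5.3 to 1.3 |
| Any skin irritation, if recorded at visits | 30% | 0.30 to 0.75 | 24.0 | 8.0 to 20.0 | 16.0 to 4.0 |

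The recorded ratio is 0.90 / 0.75 = 1.2 up to 0.90 / 0.30 = 3.0. If other routes detect events equally well in both arms, the gap is 0. The last two rows apply only if the skin sections are completed at visits.

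**Step 5. With the same checklist in both arms.** Scheduled enquiries by checklist become 89 × 3 = 267 per arm (76 × 3 = 228 after attrition), feeding 3 reviews per participant in each arm.

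**The case against.** The strongest reply has four parts.

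1. *Other routes serve both arms.* Section 3.5 says hypoglycemia, hyperglycemia and sensor risks will be monitored, section 3.5.4 sets out how adhesive reactions are managed, and section 3.6.2 gives all participants access to staff and a study physician. The recording rule also covers unscheduled calls. This stands in part: these routes may capture some CGM-only events, and serious events are likelier to surface unprompted. None of them sets a collection procedure or schedule, so they narrow the gap by an unknown amount.

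2. *The forms are not shown.* The case report forms and the items of the medical update are not reproduced, and the update could already ask about severe hypoglycemia, DKA or device problems. This stands as a limit. The finding concerns what the plan states; if such items exist, the remedy is to say so.

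3. *Mild skin irritation is not tied to visits.* This stands. A reader might infer that all skin events will be under-recorded in CGM-only. The documents do not support that, because the skin sections have no stated schedule. Only irritation severe enough for an adverse-event form falls clearly under the visit-and-call rule.

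4. *Little depends on it.* No between-arm harms test or table is planned, and the study is described as minimal risk. This also stands and limits the priority. A reader might infer a bias in the A1c or distress comparison, or a false-positive harms test. The first does not follow, because A1c kits, CGM downloads and surveys run identically in both arms. The second does not arise, because no such test is specified.

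A footnote on ONBOARD's extra contacts would help interpretation, but it would not supply the missing CGM-only reports.

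**Conclusion.** The point holds as a defect in safety data collection, of minor to moderate priority. Following the stated rule exactly gives four scheduled enquiries per ONBOARD participant and none per CGM-only participant during about weeks 2 to 11. Non-serious study-related events, including severe skin irritation, are therefore likely to be recorded more completely in ONBOARD. For milder irritation the same is possible but conditional on how the skin sections are completed.

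The direction rests on two premises: asking finds more events than not asking, and the listed survey content is complete with respect to adverse events. The size cannot be determined from the documents. On the assumed inputs it is 0.1 to 1.3 people for form-level events, so any effect on removals under section 3.7 is likely to be about one person or fewer. The larger figures, 1 to 16 people, belong only to the conditional skin-irritation case. The efficacy conclusions are not materially affected.

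**What to change.** In section 3.2 (Recording), add one short adverse-event checklist, identical in both arms, to the existing 3-, 6- and 12-month REDCap surveys. It should cover severe hypoglycemia, DKA, skin irritation (none, mild, moderate, severe), sensor-site infection, and other. Staff should follow up positive answers and apply the definitions in section 3.2; self-report alone cannot confirm DKA, which is defined partly by laboratory values. State also when the case report form skin sections are completed, in both arms.

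In section 3.1, state that the two-monthly review includes checklist answers from both arms.

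In section 2.7, state that any by-arm description of harms shows checklist-elicited events separately from those found in sessions or unscheduled contacts, with a note that ONBOARD had four extra contacts. Events found by any route should still be recorded and acted on. Restricting the description to checklist answers would be a debatable choice and is not needed.

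Cost: about five items at three existing time points (up to 267 checklists per arm), a survey amendment, and staff time to screen answers promptly. No new visits. Recall over 3 to 6 months will lose some mild events in both arms, survey non-responders will be missed, and ONBOARD participants may still recall skin problems somewhat better after discussing them. Because the first checklist comes at 3 months, it improves the record more than it speeds care.
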